Special Safety Topic	Definition / Derivation	Analysis / Summary / Listing
Reactions	
specified by MedDRA excluding the following 10 PTs:
 
 1) Embolia cutis medicamentosa 2) Injection site joint discomfort 3) Injection site joint effusion 4) Injection site joint erythema 5) Injection site joint infection 6) Injection site joint inflammation 7) Injection site joint movement impairment 8) Injection site joint pain 9) Injection site joint swelling 10) Injection site joint warmth. 
The Injection Site Reaction eCRF page captures the injection site reactions identified by the investigator. These TEAEs will be summarized within the MedDRA HLT by maximum severity or category. If more than one TEAE of injection site reaction occurs, the event with the worst value (within the individual categories: redness, swelling and pain) will be used.
 
Redness (Scored 0-4)
 
 • [0] Subject’s normal skin color, no increased redness • [1] Noticeable, but very mild redness • [2] Clearly red • [3] Bright red • [4] Dark with some scar formation 
Swelling (Scored 0-4 after running a finger over injected area)
 
 • [0] No bump • [1] Barely noticeable • [2] Clear bump but very thin • [3] Clear bump 1 mm thick • [4] Clear bump 2 mm thick or more 
Pain (including burning) (Scored 0-3)
 
 • [0] None • [1] Mild • [2] Moderate • [3] Severe 	
Period 3 (Summary): TEAE by maximum severity by PT within HLT, SAE by PT within HLT, TEAE identified by the investigator PT within HLT: by maximum severity, by maximum redness category, by maximum swelling category, by maximum pain category
 
Combined Periods 2 and 3 (Summary): TEAE by maximum severity by PT within HLT SAE by PT within HLT
 
Listing: TEAE including information collected on Injection Site Reaction eCRF page

Cerebro-	Cerebro-cardiovascular events will be externally adjudicated by the Central Events Committee (CEC)	Period 2 (Fisher’s exact test),

Special Safety Topic	Definition / Derivation	Analysis / Summary / Listing
cardiovascular Events	
at the Cleveland Clinic, as outlined in the Manual of Operations. The CEC will adjudicate investigator-reported events selected for adjudication and render an assessment as to whether the event represents a confirmed event (meeting the event definition with all necessary documentation), a non-event (does not meet the event definition and likely represents an alternative or nonevent diagnosis), or lacks sufficient documentation for confirmation of an event. All events which qualify for CEC adjudication will be used for the analysis of cerebro-cardiovascular events. The categories and subcategories of adjudicated events used for the analysis will include the following:
 
 • Cardiovascular 
 ○ Death (Cardiovascular) ○ Cardiac Ischemic Event: Myocardial Infarction and Hospitalization for Unstable Angina ○ Serious Arrhythmia ○ Hospitalization for Heart Failure ○ Hospitalization for Hypertension ○ Resuscitated Sudden Death ○ Cardiogenic Shock ○ Coronary Revascularization • Neurologic 
 ○ Cerebrovascular Event: Transient Ischemic Attack or Stroke (Hemorrhagic, Ischemic and Undetermined) • Peripheral Vascular Events 
 ○ Peripheral Arterial Event ○ Peripheral Revascularization 
Events will be analyzed using MedDRA PT nested within the CEC assessment (confirmed event, no event, or insufficient documentation for event determination) and the subcategory. Subtypes of stroke (Hemorrhagic Stroke, Ischemic Stroke, and Undetermined Stroke Type) will be displayed in the analyses nested within Cerebrovascular Event. Subtypes of Serious Arrhythmia (Atrial Arrhythmia, Ventricular Arrhythmia, Heart Block, Other, Unknown) will be displayed nested within Serious Arrhythmia.
	
Period 3 and Combined Periods 2 and 3 (Summary): TEAE by PT within Subcategory
 
Listing: TEAE

Major Adverse Cerebro-Cardiovascular Events (MACE)	
MACE (requiring adjudication as defined above) is defined as:
 
 • Vascular Death (including cardiovascular and cerebro-vascular causes excluding hemorrhagic deaths outside of the central nervous system) • Non-fatal myocardial infarction • Non-fatal stroke (subtypes: hemorrhagic stroke, ischemic stroke, undetermined stroke type) 	
Period 2 (Fisher’s exact test), Period 3 and Combined Periods 2 and 3 (Summary): TEAE by maximum severity by PT within category

Special Safety Topic	Definition / Derivation	Analysis / Summary / Listing
	
Where,
 
 • Vascular death should be captured as an Event on Adjudication - Death eCRF page with Adjudication Death Type = ‘Cardiovascular’. • Non-fatal myocardial infarction should be captured as an Event on Adjudication - Cardiac Ischemic Event eCRF page with Type of Ischemic Event = “Myocardial Infarction” and the Event is NOT on Adjudication - Death eCRF page. • Non-fatal strokes (ischemic, hemorrhagic) should be captured as an Event on Adjudication - Cerebrovascular Event eCRF page with Stroke Cerebrovascular Event Subtype in one of the following categories: hemorrhagic stroke, ischemic stroke, undetermined stroke type, and the Event is NOT on Adjudication - Death eCRF page. Subcategories of non-fatal stroke (Hemorrhagic Stroke, Ischemic Stroke, and Undetermined Stroke Type) will be displayed nested within non-fatal stroke category. 	
Listing: TEAE

Malignancies	
Malignancy is defined using PTs from the Malignant or unspecified tumors SMQ as specified in MedDRA (SMQ: 20000091, which includes the sub-SMQs:
 
 • 20000194 [Malignant tumours], including sub-SMQs of 20000227 [Haematological malignant tumours] and 20000228 [Non-haematological malignant tumours] • 20000195 [Tumours of unspecified malignancy], including sub-SMQs of 20000229 [Haematological tumours of unspecified malignancy] and 20000230 [Non-haematological tumours of unspecified malignancy] 
Events will be summarize by the following categories:
 
 • Nonmelanoma Skin Cancer (NMSC) 
 ○ Basal Cell Carcinoma, PTs include: 
 ▪ Basal cell carcinoma ▪ Basosquamous carcinoma ▪ Basosquamous carcinoma of skin ○ Squamous Cell Carcinoma, PTs include: 
 ▪ Squamous cell carcinoma of skin ▪ Bowen’s disease ▪ Lip squamous cell carcinoma ▪ Skin squamous cell carcinoma metastatic ▪ Keratoacanthoma • Malignancies excluding NMSC: all PTs in the Malignant or unspecified tumors SMQ excluding the 8 defined NMSC PTs. 	
Period 2 (Fisher’s exact test), Period 3 and Combined Periods 2 and 3 (Summary) : TEAE by PT within category
 
Listing: TEAE

Special Safety Topic	Definition / Derivation	Analysis / Summary / Listing
Depressions	Depression is defined using the PTs from the Depression and suicide/self-injury SMQ as specified in MedDRA (SMQ: 20000035, which includes the sub-SMQs: 20000037 [Suicide/self-injury] and 20000167 [Depression (excl suicide and self-injury)]).	
Period 2 (Fisher’s exact test), Period 3 and Combined Periods 2 and 3 (Summary): TEAE by PT within SMQ and sub-SMQ
 
Listing: TEAE (included in the same listing with hepatic, cytopenia and interstitial lung disease AESIs)

Inflammatory Bowel Disease (IBD)	
IBD will be identified using the following subcategory and MedDRA PTs. The narrow terms are considered IBD
 
IBD (Narrow terms)
 
 • Inflammatory Bowel Disease: Inflammatory bowel disease • Crohn’s Disease: Crohn’s disease • Ulcerative Colitis: Acute haemorrhagic ulcerative colitis; Colitis ulcerative; Proctitis ulcerative 
Non-Specific Terms (Events That Can Occur with IBD (Broad Terms)): The PTs in this category are listed in Appendix 10.
	
Period 2 (Fisher’s exact test), Period 3 and Combined Periods 2 and 3 (Summary): TEAE by PT within subcategory
 
Listing: TEAE

Interstitial Lung Disease (ILD)	
ILD is defined using the following terms:
 
 • Broad and narrow terms in the Interstitial lung disease SMQ (20000042) • Additional 6 PTs from Eosinophilic pneumonia SMQ (20000157): 
 ○ Angiolymphoid hyperplasia with eosinophilia (Narrow) ○ Eosinophilic bronchitis (Narrow) ○ Hypereosinophilic syndrome (Narrow) ○ Loeffler’s syndrome (Narrow) ○ Pulmonary eosinophilia (Narrow) ○ Pulmonary vasculitis (Narrow) 	
Listing: TEAE (included in the same listing with hepatic, depression and interstitial lung disease AESIs)

Abbreviations: AE = adverse event; AESI = adverse event of special interest; eCRF = electronic case report form; HLT = high-level term; OI =opportunistic infection; PT = preferred term; SAE = serious adverse event; TEAE = treatment emergent adverse event.

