### 7.1. Discontinuation from Study Treatment

#### 7.1.1. Discontinuation from Study Treatment

The following criteria must be followed for discontinuation from study treatment. Patients will enter into the Post-Treatment Follow-Up Period (Period 4) if they discontinue from study treatment.

- [1] Discontinuation of the investigational product for abnormal liver tests should be considered by the investigator when a patient meets one of the following conditions, after consultation with the Lilly designated medical monitor:
  - ALT or AST >8xULN
  - ALT or AST >5xULN for more than 2 weeks
  - ALT or AST >3xULN and total bilirubin level >2xULN or prothrombin time >1.5xULN
  - ALT or AST >3xULN with the appearance of fatigue, nausea, vomiting, right upper-quadrant pain or tenderness, fever, rash, and/or eosinophilia (>5%)
  - alkaline phosphatase >2.5xULN and total bilirubin >2xULN
  - alkaline phosphatase >2.5xULN with the appearance of fatigue, nausea, vomiting, right upper quadrant pain or tenderness, fever, rash, and/or eosinophilia (>5%)
- [2] Other laboratory tests (**Note:** Laboratory test(s) that may result in discontinuation based on a single result may be repeated only once if there is a technical error or clinical reason to believe a result may need to be retested. Laboratory tests can only be repeated after consultation with Lilly medical. Investigational product should not be administered in these cases until retest result is available.):
  - Neutrophil (segmented) counts (see safety monitoring for neutropenia in Section [8.4.10.1](#)):

- $<500$  cells/ $\mu\text{L}$  ( $<0.50 \times 10^3/\mu\text{L}$  or  $<0.50$  GI/L)
  - $\geq 500$  and  $<1000$  cells/ $\mu\text{L}$  ( $\geq 0.50 \times 10^3/\mu\text{L}$  and  $<1.00 \times 10^3/\mu\text{L}$  or  $\geq 0.50$  GI/L and  $<1.00$  GI/L) (based on 2 test results; the second test performed within 1 week from knowledge of the initial result)
  - $\geq 1000$  and  $<1500$  cells/ $\mu\text{L}$  ( $\geq 1.00 \times 10^3/\mu\text{L}$  and  $<1.50 \times 10^3/\mu\text{L}$  or  $\geq 1.00$  GI/L and  $<1.50$  GI/L) (based on 3 test results as specified in Section 8.4.10.1)
    - AND - a concurrent infection
  - Total WBC count  $<2000$  cells/ $\mu\text{L}$  ( $<2.00 \times 10^3/\mu\text{L}$  or  $<2.00$  GI/L).
  - Lymphocyte count  $<500$  cells/ $\mu\text{L}$  ( $<0.50 \times 10^3/\mu\text{L}$  or  $<0.50$  GI/L).

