#### **8.2.2. Adverse Events of Special Interest**

The following adverse events of special interest (AESIs) will be used to determine the safety and tolerability of ixekizumab over the range of doses selected for this clinical study.

The AESIs for ixekizumab are:

- cytopenias (leukopenia, neutropenia, and thrombocytopenia)
- clinically significant hepatic events and/or significant elevations in liver function test changes/enzyme elevations (ALT, AST, bilirubin, and alkaline phosphatase)
- infections
- injection-site reactions
- allergic reactions/hypersensitivities
- cerebrocardiovascular events
- malignancies
- IBD
- depression.

Sites will provide details on some of these AEs as instructed on the CRF. Investigators will also educate patients and/or caregivers about the symptoms of allergic/hypersensitivity reactions and will provide instructions on dealing with these reactions (see also Section 6.6.1). A blood sample is to be collected as soon as possible for any patient who experiences an AE of a potential systemic allergic /hypersensitivity reactions during the study as judged by the investigator.

Data on preferred terms associated with cerebrocardiovascular events (defined as death, cardiac ischemic events including MI and hospitalization for unstable angina, hospitalization for heart failure, serious arrhythmia, resuscitated sudden death, cardiogenic shock, coronary revascularization procedure, stroke/transient ischemic attack, peripheral revascularization procedure, and peripheral arterial event and hospitalization for hypertension) will be collected, and these events and any deaths will be adjudicated by an external Clinical Events Committee (CEC) made up of a chairman, 2 cardiologists, and a neurologist.

Data on suspected IBD, as identified by events possibly indicative of ulcerative colitis and Crohn's disease, will be collected and the events will be adjudicated by an external CEC with expertise in IBD.

The role of external CECs is to adjudicate defined clinical events in a blinded, consistent, and unbiased manner throughout the course of a study. The purpose of the CEC for adjudication of cerebrocardiovascular events and the CEC for adjudication of suspected IBD events is to ensure that all reported events are evaluated uniformly by a single group.

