#### **8.4.10. Safety Monitoring**

Lilly will periodically review evolving aggregate safety data within the study by appropriate methods.

If a study patient experiences elevated ALT  $\geq 3$ xULN, alkaline phosphatase  $\geq 2$ xULN, or elevated total bilirubin  $\geq 2$ xULN, clinical and laboratory monitoring is to be initiated by the investigator. Details for hepatic monitoring depend upon the severity and persistence of observed laboratory test abnormalities. For other AESIs or abnormal lab results, please refer to the appropriate protocol section that addresses these topics. To ensure patient safety and comply with regulatory guidance, the investigator is to consult with the Lilly clinical research physician/clinical research scientist regarding collection of specific recommended clinical information and follow-up laboratory tests (see [Appendix 4](#)).

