	
Elevated hepatic criteria: maximum ALT $\geq 3 \times \text{ULN}$ and maximum total bilirubin $\geq 2 \times \text{ULN}$ using Performing Lab Reference Ranges. Listing of patients who meet any of the following criteria:
 
 Elevated hepatic criteria: defined as maximum ALT $\geq 3 \times \text{ULN}$ and maximum total bilirubin $\geq 2 \times \text{ULN}$ An ALT or AST $\geq 3 \times \text{ULN}$ An alkaline phosphatase (ALP) $> 1.5 \times \text{ULN}$ A total bilirubin $\geq 2 \times \text{ULN}$ 
The listing will include: patient demographics, concomitant medications, ALT/AST/ALP/total bilirubin/GGT by visit, treatment start and stop dates, and reason for treatment discontinuation.
	
Period 2 (Fisher’s exact test), Period 3, and Period 4 (Summary): Elevated hepatic criteria
 
Listing: Elevations in hepatic laboratory tests

	
Evaluation of Drug-Induced Serious Hepatotoxicity (eDISH) plot: use maximum ALT measurement and maximum total bilirubin measurement with patients having at least one postbaseline ALT and total bilirubin, which contributes one point to the plot. The measurements do not need to be taken at the
	
Period 2: eDISH plot (to be prepared in Spotfire)

Special Safety Topic	Definition / Derivation	Analysis / Summary / Listing
	same blood draw.	
Cytopenias	
Cytopenias are defined using the PTs from the following 2 sub-SMQs of the Haematopoietic cytopenias SMQ (20000027) as specified in MedDRA:
 
 • Broad and narrow terms in the Haematopoietic leukopenia (20000030) • Broad and narrow terms in the Haematopoietic thrombocytopenia (20000031) 	
Period 2 (Fisher’s exact test) and Period 3 (Summary): Combined Periods 2 and 3 (Summary): TEAE by PT within sub-SMQ Listing: TEAE (included in the same listing with hepatic, depression and interstitial lung disease AESIs)

Infections	
Infections are events including all infections (defined using all the MedDRA PTs from the Infections and infestations OSC), serious infections, potential opportunistic infections, and infections resulting in anti-infective medication administration (i.e. antibacterial, antivirals, antifungals, antiparasitic treatments).
	
Period 2 (Fisher’s exact test), Period 3 (Summary), Combined Periods 2 and 3 (Summary): SAE by PT

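### The SAP's joint transaminase–bilirubin summary and eDISH plot omit AST, so an AST-driven case is missing from the only table that counts the joint signal by arm

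*SAP*

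**What the plan says.** SAP section 6.12.3.1, Table RHBV.6.8 (Hepatic), sets out several laboratory analyses.

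- **Combined criterion.** "Elevated hepatic criteria: maximum ALT" at or above 3xULN together with maximum total bilirubin at or above 2xULN. It is compared by Fisher's exact test in Period 2 and summarised in Periods 3 and 4. AST does not appear.
- **eDISH plot, Period 2.** The instruction is to "use maximum ALT measurement and maximum total bilirubin measurement with patients having at least one postbaseline ALT and total bilirubin". Each such patient contributes one point, and the two maxima may come from different blood draws.
- **Listing.** A patient is listed for meeting the combined criterion, or for ALT or AST at or above 3xULN, or for bilirubin at or above 2xULN, or for raised alkaline phosphatase. AST and bilirubin are shown by visit.
- **Single-analyte analyses.** ALT or AST at 3, 5, 10 and 20xULN and bilirubin at 1.5 and 2xULN (Periods 2 and 3). Shift tables cover all four analytes (Periods 2, 3 and the two combined).

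The protocol refers to liver tests in three places. Section 7.1.1 includes the condition "ALT or AST >3xULN and total bilirubin level >2xULN or prothrombin time >1.5xULN", under the introduction "Discontinuation of the investigational product for abnormal liver tests should be considered by the investigator when a patient meets one of the following conditions". Section 8.2.2 defines the hepatic events of special interest as "clinically significant hepatic events and/or significant elevations in liver function test changes/enzyme elevations (ALT, AST, bilirubin, and alkaline phosphatase"). Section 8.4.10 sets a monitoring trigger that begins "If a study patient experiences elevated ALT" and goes on to alkaline phosphatase and bilirubin, without naming AST.

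**The concern.** AST is present in the protocol's discontinuation condition, in its definition of hepatic events of special interest, and in the SAP's threshold tables, shift tables and listing. It is absent only where the SAP joins a transaminase to bilirubin. The readable text gives no reason for this.

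The joint summary and the eDISH plot exist to pick out patients with both elevations. If a case can qualify under section 7.1.1 through AST and still be a non-case in the table that counts joint elevations by arm, the reader of that table is not told about it. The same patient could even appear in the protocol-deviation table (item D1 of SAP Table RHBV.6.12, failure to consult when the hepatic laboratory criteria were met) while being absent from the joint hepatic table.

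**Working it through.** The plan states no figure for this point, so there is nothing to reproduce. The check is to classify patients under each definition.

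**Definitions, in multiples of ULN**

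- Protocol 7.1.1, enzyme-plus-bilirubin limb: (ALT > 3 or AST > 3) and bilirubin > 2.
- SAP combined criterion: ALT ≥ 3 and bilirubin ≥ 2.
- SAP criterion with AST added: (ALT ≥ 3 or AST ≥ 3) and bilirubin ≥ 2.

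**One illustrative patient: ALT 2.5, AST 6, bilirubin 2.5**

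| Analysis | Result |
|---|---|
| Protocol 7.1.1 limb | met (6 > 3 and 2.5 > 2) |
| SAP combined criterion | not met (2.5 < 3) |
| With AST added | met (6 ≥ 3 and 2.5 ≥ 2) |
| AST threshold table, Periods 2 and 3 | counted at 3x and 5x |
| Bilirubin threshold table, Periods 2 and 3 | counted at 1.5x and 2x |
| Shift tables, Periods 2, 3 and combined | AST and bilirubin both shown |
| Listing | included, through AST and through bilirubin |
| eDISH, Period 2 | plotted, at 2.5 on the enzyme axis |

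**Grid check.** ALT and AST were each set to 1.5, 3 and 3.5, and bilirubin to 1.5, 2 and 2.5, giving 3 × 3 × 3 = 27 combinations. Adding AST changes the SAP classification in 4 of them: ALT 1.5 with AST 3 or 3.5 and bilirubin 2 or 2.5. One of these 4 (AST 3.5, bilirubin 2.5) also meets the protocol limb; the other three lie on a threshold, where the SAP counts equality and the protocol does not. In the opposite direction, 8 combinations meet the SAP criterion but not the protocol limb, all because ALT is exactly 3 or bilirubin exactly 2.

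**Whether the other tables replace the joint count.** The threshold and shift tables treat each analyte separately. One patient in the AST row and one in the bilirubin row may or may not be the same person. Only a by-patient listing settles that, and a listing gives no count by arm.

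**Period 4.** Section 6.12.3.1 says special-topic summaries are generally not given for follow-up, apart from hepatic laboratory tests. The threshold tables stop at Period 3 and the shift tables at the combined Periods 2 and 3, so the ALT-only criterion is the one hepatic summary in Table RHBV.6.8 assigned to Period 4. Section 6.12.4 removes ALT, AST, bilirubin and alkaline phosphatase from the general abnormal-value summary. That exclusion is worded for treatment-emergent values; if it were read as leaving follow-up-emergent AST in place, the result would still be a single-analyte count above ULN.

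**Size on the test.** Assume 80 per arm, the planned group size. For k events against 0, the two-sided Fisher p-value is 2 × C(80,k)/C(160,k).

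- k = 1: 2 × 80/160 = 1.00
- k = 2: 0.497
- k = 5: 0.059
- k = 6: 0.028, the first below 0.05

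**The case against.** The strongest reply is that little is lost. In Periods 2 and 3 the example patient is counted in two threshold tables, both Fisher-tested in Period 2, appears in the shift tables, and is listed with values by visit. The eDISH plot drops nobody; it places the patient at the ALT value with raised bilirubin visible, and the SAP defines no case region on it. All of this stands. A reader might infer that the SAP counts such a patient as having no hepatic event at all. The documents do not support that: the statement is true only of the combined row.

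Second, a reader might infer that the SAP contradicts the protocol. It does not. Section 7.1.1 is a prompt for the investigator to consider stopping treatment, one of six conditions, with a prothrombin-time alternative and strict inequalities. It is not an analysis endpoint, and section 8.4.10 does not name AST. Adding AST to the SAP row would bring it closer to 7.1.1 without reproducing it.

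Third, AST can rise from muscle, so ALT alone is a defensible choice for specificity. The SAP also defers to a program safety analysis plan that is not among the documents and may give the reason. Both points are fair. They support keeping the ALT-only row; they do not explain why no either-transaminase count is shown beside it.

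What survives is that the joint count by arm cannot be recovered from the single-analyte tables, and that in Period 4 those tables are not assigned.

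**Conclusion.** The concern holds as a gap in case identification. An AST-driven joint elevation with ALT below 3xULN is a non-event in the combined summary and is misplaced, not omitted, on eDISH. The laboratory analyses reveal it through separate tables and listings in Periods 2 and 3 and, on the reading of section 6.12.4 given above, through listings alone in Period 4.

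Its size in patients cannot be estimated, because the documents give no rate for the pattern. It is tempting to say that one missed case would change the hepatic conclusion. The SAP attaches no decision rule to this row, and at an assumed 80 per arm 1 v 0 gives p = 1.00, so that reading is not supported. This is an inexpensive improvement to the safety analysis, not an error that threatens a conclusion.

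**What to change.** In SAP Table RHBV.6.8:

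- Keep the ALT-only row. Add a second row for ALT or AST at or above 3xULN with total bilirubin at or above 2xULN, in Periods 2, 3 and 4.
- Add an eDISH version whose enzyme axis is the larger of the ALT and AST multiples of their own ULN.
- Give a sentence on why ALT alone is used for the existing row.

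The cost is one derivation on data already collected. Section 6.12.3.1 allows changes to special-topic analyses to be documented in the program safety analysis plan without amending the SAP. SAP version 3 was approved after unblinding, so the added row should be labelled with the date it was introduced. The downside is a few more patients to review, including AST rises of muscle origin; the CPK already measured (Protocol Appendix 3) can be used to annotate these.

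No clinical threshold changes. The triggers in Protocol 7.1.1 and 8.4.10 differ in whether AST is named and in their inequalities; the sponsor should reconcile those passages or state that the difference is intended.
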